8.3 Adjustments for Covariates and Factors to be Included in Analyses

The following covariates and factors are used in ANCOVA models. For details of their inclusion in the models, see the specific analysis section.

- Baseline value of interest
- Treatment group: Eze/Ato, Ato
- History of statin administration: Yes (≥ 4 weeks), No (< 4 weeks, naïve)

Document: Document path and title

Template No.: CCI

Reference: CCI

Effective Date: 15Oct2021

- Yes if 'Is the patient under statin treatment?' is 'Yes for 4 weeks or more from today' from 'Medical history related to dyslipidemia risk factors' page of eCRF
- No if 'Is the patient under statin treatment?' is 'Yes, but for less than 4 weeks from today' or 'No' from 'Medical history related to dyslipidemia risk factors' page of eCRF

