5.1 Inclusion Criteria

Participants are eligible to be included in the study only if all of the following criteria apply:

1. Patients who are ≥ 30 years old.
2. Patients with very high-risk*
*: clinical or unequivocal on imaging ASCVD. ASCVD includes previous ACS (MI or UA), stable angina, coronary revascularization (percutaneous coronary intervention (PCI), coronary artery bypass graft surgery (CABG), and other arterial revascularization procedures), stroke and transient ischaemic attack (TIA), and peripheral arterial disease (Mach F 2020).
3. Patients (a) who failed to achieve LDL-C lower than 70 mg/dL with low and/or moderate intensity^{\$} statin mono therapy for ≥ 4 weeks or (b) who are statin-naïve or have not been on a stable (unchanged) statin regimen for at least 4 weeks prior to enrollment.
\$: rosuvastatin < 20 mg, atorvastatin < 40 mg, and all dose of pitavastatin, simvastatin, lovastatin, pravastatin, and fluvastatin (Stone NJ 2014).
4. Patients with LDL-C levels ≥ 70 mg/dL
5. Patients who are willing to maintain TLC throughout the study.
6. Patients who are willing to provide written informed consent prior to study enrollment.

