6.3.1 Stratified block randomization

The randomization code will be set so that the test group and control group can be assigned in a 1:1 ratio by the stratified block randomization method for each institution and using statin administration history as a stratification factor.

Inclusion criterion No. 3 is the stratification factor, and the classification is as follows:

(a) patients who failed to achieve their target LDL-C goals with low and/or moderate intensity statin mono therapy for ≥ 4 weeks

(b) patients who are statin-naïve or have not been on a stable (unchanged) statin regimen for at least 4 weeks prior to enrollment

However, in the case of (b) patients, less than 40% of each group should be recruited.

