8.5 Examination of Subgroups

Subgroup analyses will be conducted as stated in the exploratory analysis section 15.3.

The following subgroups will be assessed and described within the exploratory analysis sections:

- Sex: Female, Male
- Age (years): <65, ≥65
- History of statin administration: Yes, No (refer to section 8.3 for categorization)
- Status of a dose up-titration at Week 6: Yes, No
 - Yes (if study treatment dose is increased at Visit 3)
 - No (if study treatment dose is unchanged at Visit 3)

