8.6 Randomization Schedule

In Visit 2, randomization is performed on patients who meet the inclusion criteria and do not meet any of the exclusion criteria and will be distributed 1:1 between test group (arm Eze/Ato) and control group (arm Ato).

Document: Document path and title

Template No.: CCI

Reference: CCI

Effective Date: 15Oct2021

All patients will be centrally assigned to randomized study intervention using an interactive web response system (IWRS).

Stratified block randomization

The randomization code will be set so that the test group and control group can be assigned in a 1:1 ratio by the stratified block randomization method for each institution and using statin administration history as a stratification factor.

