15.1.2 Primary Analysis of Primary Effectiveness Variable

The primary endpoint analysis will be performed on the FAS.

The statistical hypothesis of this study is as follows.

$$H_0: \mu_t - \mu_c = 0 \text{ vs. } H_1: \mu_t - \mu_c \neq 0$$

Document: Document path and title

Template No.: CCI

Reference: CCI

Effective Date: 15Oct2021

μ_t = Percentage change in LDL-C from baseline to 6 weeks in ezetimibe/atorvastatin 10/40 mg
 μ_c = Percentage change in LDL-C from baseline to 6 weeks in atorvastatin 40 mg

The primary endpoint will be analyzed by fitting an ANCOVA model with treatment group (Eze/Ato, Ato) and history of statin administration (Yes, No) as fixed effects and baseline LDL-C as a covariate. In addition to descriptive statistics for LDL-C at each visit and its percentage change from baseline by treatment group, least squares (LS) means for each treatment group with corresponding standard errors (SEs) and treatment differences of LS means with corresponding two-sided 95% confidence interval (CI) and p-value which will be derived from the fitted model will be presented. If the upper limit of the 95% two-sided CI for the corresponding treatment difference (Eze/Ato - Ato) is less than 0, Eze/Ato is considered superior to Ato.

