Effective Date: 15Oct2021

Item	Statistics	Eze/Ato (N=00)	Ato (N=00)	Total (N=00)
	[Min – Max]	[00.00 - 00.00]	[00.00 - 00.00]	[00.00 - 00.00]
ACS	Nx	00	00	00
Yes	n(%)	00 (00.00)	00 (00.00)	00 (00.00)
No	n(%)	00 (00.00)	00 (00.00)	00 (00.00)
Stable angina	Nx	00	00	00
Yes	n(%)	00 (00.00)	00 (00.00)	00 (00.00)
No	n(%)	00 (00.00)	00 (00.00)	00 (00.00)
Coronary revascularization	Nx	00	00	00
Yes	n(%)	00 (00.00)	00 (00.00)	00 (00.00)
No	n(%)	00 (00.00)	00 (00.00)	00 (00.00)
Stroke	Nx	00	00	00
Yes	n(%)	00 (00.00)	00 (00.00)	00 (00.00)
No	n(%)	00 (00.00)	00 (00.00)	00 (00.00)
Transient ischemic attack	Nx	00	00	00
Yes	n(%)	00 (00.00)	00 (00.00)	00 (00.00)
No	n(%)	00 (00.00)	00 (00.00)	00 (00.00)
Peripheral arterial disease	Nx	00	00	00
Yes	n(%)	00 (00.00)	00 (00.00)	00 (00.00)
No	n(%)	00 (00.00)	00 (00.00)	00 (00.00)
Other clinical or unequivocal ASCVD on imaging	Nx	00	00	00
Yes	n(%)	00 (00.00)	00 (00.00)	00 (00.00)
No	n(%)	00 (00.00)	00 (00.00)	00 (00.00)
Family history status	Nx	00	00	00
Yes	n(%)	00 (00.00)	00 (00.00)	00 (00.00)
No	n(%)	00 (00.00)	00 (00.00)	00 (00.00)
Family history [a]	Nx	00	00	00
Father	n(%)	00 (00.00)	00 (00.00)	00 (00.00)
Mother	n(%)	00 (00.00)	00 (00.00)	00 (00.00)
Brothers/sisters	n(%)	00 (00.00)	00 (00.00)	00 (00.00)
Other	n(%)	00 (00.00)	00 (00.00)	00 (00.00)
History of stain administration	Nx	00	00	00
Yes (≥4 weeks)	n(%)	00 (00.00)	00 (00.00)	00 (00.00)
No (<4 weeks or naïve)	n(%)	00 (00.00)	00 (00.00)	00 (00.00)
<4 weeks	n(%)	00 (00.00)	00 (00.00)	00 (00.00)
Naïve	n(%)	00 (00.00)	00 (00.00)	00 (00.00)

Document: Document path and title

Template No.: CCI

Reference: CCI

Effective Date: 15Oct2021

Item	Statistics	Eze/Ato (N=00)	Ato (N=00)	Total (N=00)
Baseline LDL-C (mg/dL)	Nx	00	00	00
	Mean \pm SD	00.00 \pm 00.00	00.00 \pm 00.00	00.00 \pm 00.00
	Median	00.00	00.00	00.00
	Q1, Q3	00.00, 00.00	00.00, 00.00	00.00, 00.00
	[Min – Max]	[00.00 - 00.00]	[00.00 - 00.00]	[00.00 - 00.00]
Baseline LDL-C categories	Nx	00	00	00
<130	n(%)	00 (00.00)	00 (00.00)	00 (00.00)
\geq 130 to <160	n(%)	00 (00.00)	00 (00.00)	00 (00.00)
\geq 160	n(%)	00 (00.00)	00 (00.00)	00 (00.00)
Baseline HDL-C (mg/dL)	Nx	00	00	00
	Mean \pm SD	00.00 \pm 00.00	00.00 \pm 00.00	00.00 \pm 00.00
	Median	00.00	00.00	00.00
	Q1, Q3	00.00, 00.00	00.00, 00.00	00.00, 00.00
	[Min – Max]	[00.00 - 00.00]	[00.00 - 00.00]	[00.00 - 00.00]
Baseline non-HDL-C (mg/dL)	Nx	00	00	00
	Mean \pm SD	00.00 \pm 00.00	00.00 \pm 00.00	00.00 \pm 00.00
	Median	00.00	00.00	00.00

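### The statin-history factor in the ANCOVA is coded from time on statin, not from the (a)/(b) stratum used for randomisation, so some stratum (b) patients may be modelled with (a)

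*SAP*

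**What the plan says.** **Randomisation.** Protocol 6.3.1 states that "Inclusion criterion No. 3 is the stratification factor". Under that criterion (Protocol 5.1), class (a) is patients not at goal after at least 4 weeks of low- or moderate-intensity statin monotherapy. Class (b) is patients "who are statin-naïve or have not been on a stable (unchanged) statin regimen for at least 4 weeks prior to enrollment". Class (b) is capped: "in the case of (b) patients, less than 40% of each group should be recruited".

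**Analysis.** SAP 15.1.2 fits the primary ANCOVA with treatment and "history of statin administration (Yes, No) as fixed effects and baseline LDL-C as a covariate"; SAP 15.2.3 does the same for the continuous secondary endpoints other than triglycerides. SAP 8.3 defines the factor: "Yes if 'Is the patient under statin treatment?' is 'Yes for 4 weeks or more from today". It is No if the same item records statin use for under 4 weeks or none. SAP 8.5 reuses this coding for subgroups: "History of statin administration: Yes, No (refer to section 8.3 for categorization".

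**Link between the two.** SAP 8.6 describes the randomisation as "using statin administration history as a stratification factor" and does not repeat the (a)/(b) definition. SAP 4.5 declares no change from the protocol. In the shell for Table 10 the second category is "No (<4 weeks or naïve", split only into those two components. No shell tabulates the IWRS stratum.

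**The concern.** The two variables carry almost the same name but rest on different facts. The stratum depends on whether the regimen was unchanged for 4 weeks. The model factor depends only on whether the patient was on any statin for 4 weeks. Someone treated for months whose drug or dose changed two weeks before enrolment belongs to (b) under the protocol and can be Yes in the model, pooled with (a).

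Three things are at stake:

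- **Precision.** If these patients respond differently from (a), the model leaves out part of a variable that the randomisation balanced, and the standard error is too large.
- **Subgroups.** The exploratory statin-history analyses (Tables 90-117) would not be the randomised strata.
- **Reporting of the cap.** Protocol Appendix 6 names the stratum (b) ratio as a possible reason for extra enrolment, yet Table 10 could not show that ratio.

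Bias is not at stake. The statin history is collected at Visit 1 (Schedule of Activities), so both classifications precede treatment, and leaving out a pre-treatment variable does not shift the randomised comparison in a linear model.

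**Working it through.** **1. The plan's own figure.** Protocol 9.5 uses a difference of 10, SD 19, two-sided alpha 0.05 and 80% power: n = 2 × (1.96 + 0.842)² × 19² / 10² = 56.69, so 57 per group. For 10% dropout, 56.69 / 0.9 = 62.99, so 63 per group and 126 in total. The stated size reproduces; power at 57 per group is 0.802.

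**2. How large (b) can be.** 0.40 × 63 = 25.2, so at most 25 per arm and 50 in total (50/126 = 39.7%).

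**3. Closed-form check, baseline LDL-C left out.** Let m be the share of (b) coded Yes, D the difference in mean percentage change between strata, P = 1 − 0.4(1 − m) the proportion coded Yes, and f = 0.4m / P the share of those who belong to (b). Then

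residual variance = 19² + D² × P × f(1 − f).

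The values of m and D are assumptions, and all of (b) is given the same response. For m = 0.25 and D = 20: P = 0.70, f = 0.143, added variance = 400 × 0.70 × 0.143 × 0.857 = 34.3, SD = √395.3 = 19.88.

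Power at 57 per group:

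| m | D = 10 | D = 20 | D = 30 |
|---|---|---|---|
| 0 | 0.802 | 0.802 | 0.802 |
| 0.10 | 0.798 | 0.786 | 0.766 |
| 0.25 | 0.793 | 0.766 | 0.723 |
| 0.50 | 0.786 | 0.740 | 0.669 |

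**4. Simulation with baseline in the model.** Documented inputs: SD 19, effect −10, 1:1 allocation within stratum. Assumed inputs: 126 analysed, (b) = 50, naive patients 25 points lower than (a), and 5, 10 or 25 discordant patients (10%, 20%, 50% of (b)). Each setting had 4,000-6,000 simulated trials, so the Monte Carlo error of a power near 0.80 is about √(0.8 × 0.2 / 4000) = 0.006. Baseline was either independent of stratum or 0.8 SD higher in the eCRF No patients.

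| Discordant patients respond like | eCRF factor (5 / 10 / 25 discordant) | IWRS stratum alone | Both terms |
|---|---|---|---|
| Naive (shift −25) | 0.80 / 0.78-0.79 / 0.74-0.75 | 0.82-0.84 | 0.82-0.84 |
| In between (shift −12) | 0.80-0.82 | within 0.01 of eCRF | 0.82 |
| Stratum (a) (shift 0) | 0.82-0.83 | 0.77-0.80 | 0.82-0.83 |

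In the naive-like case the mean SE is 3.50 / 3.60 / 3.82 against 3.39 with the IWRS stratum. The ratios are 1.03, 1.06 and 1.13.

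**5. Sensitivity of the naive-like case.**

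- A 15-point gap gives 0.82 / 0.81 / 0.80 against 0.83.
- (b) = 25 of 126 (20%), with the same discordant shares and the 25-point gap, gives 0.81 / 0.81 / 0.78 against 0.83-0.84.
- With a single discordant patient the two-term model still has power 0.83.

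**6. Validity.** The mean estimate is −9.9 to −10.1 throughout. Type I error with the eCRF factor is 0.032-0.046, on the conservative side because the model SE exceeds the true one. With 25 naive-like discordant patients and no effect, the model SE is 3.83 against an empirical 3.64.

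**7. The cap.** With 50 patients in (b), 10 of them discordant, Table 10 would show 50 − 10 = 40 in the No category: 40/126 = 31.7% instead of 39.7%.

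**The case against.** The strongest reply is that the damaging case is the least likely one. By the SAP's coding a discordant patient has been on a statin for at least 4 weeks, so none is naive. Protocol 9.5 itself says that statin LDL-C lowering appears by 2 weeks and peaks by 4. The Visit 1 value is then largely a treated baseline, as in (a), and the planned coding matches or beats the IWRS stratum alone. This stands, and it is why swapping one factor for the other is not the best remedy. It does not affect the two-term model, which stays within simulation error of the better option in every case.

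Other points:

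- **The eCRF and its completion guide are not available.** A site may answer less than 4 weeks after a change of regimen, so there may be no discordant patients. This stands; the concern is conditional on it.
- **Baseline LDL-C might recover the loss.** When discordant patients were also given a naive-like baseline, power under the eCRF factor was still 0.79 and 0.76 in the two settings run, against 0.82-0.83.
- **Analysing 126 ignores dropout.** Absolute powers are about 0.03-0.04 too high. With 114 analysed, the two-term model still held up.
- **The cap is controlled by tracking registration, not by Table 10.** True. The loss is in what the report can show, not in control of enrolment.
- **The protocol's model names only statin history, so the SAP may be following it.** Possible. But Protocol 6.3.1 uses the same label for the stratification factor, so the ambiguity needs settling.
- **A model whose terms depend on observed discordance is awkward.** The rule uses pre-treatment classifications only and can be written in advance. If they coincide, the second term is redundant in any case.

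**Conclusion.** The concern holds. The SAP's model factor and the randomisation stratum are defined differently under nearly the same name, and neither the text nor any planned output maps one to the other. The consequence is modest: no bias, no inflation of type I error, and a possible loss of precision.

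The size depends on two unknowns, the number of discordant patients and how they respond. With 5 to 25 discordant patients of 50 in (b), a 25-point gap and a naive-like response, the interval is 3% to 13% wider and power falls to between 0.80 and 0.74, against 0.82-0.84. With a 15-point gap the loss is 0.01-0.03. With an intermediate response it is at most about 0.02 against the two-term model, and with an (a)-like response there is none. The subgroup labelling and the reporting of the (b) share are affected whenever discordance is above zero. The change is worth making because it is nearly free, not because serious harm has been shown.

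**What to change.** Before database lock:

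1. In SAP 8.3, 15.1.2 and 15.2.3, make the IWRS stratum, class (a) or (b) of inclusion criterion 3, the model factor. Add the eCRF category as a second term if at least one patient is classified differently, and omit it if the two coincide.
2. In SAP 8.6, state the (a)/(b) definition and say how it differs from the eCRF item.
3. Add to Table 10 a cross-tabulation of IWRS stratum against the eCRF item, by arm.
4. Present the exploratory statin-history subgroup (SAP 8.5, Tables 90-117) by IWRS stratum.

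The cost is SAP wording, one variable the IWRS already holds, one extra block of table rows and at most one degree of freedom. No new data are needed. If the two classifications agree for every patient, the analysis is unchanged.

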9.5 Sample Size Determination

The statistical hypothesis of this study is as follows.

$$H_0: \mu_t - \mu_c = 0 \text{ vs. } H_1: \mu_t - \mu_c \neq 0$$

$$\mu_t = \text{Percentage change in LDL-C from baseline to 6 weeks in ezetimibe/atorvastatin 10/40 mg}$$

$$\mu_c = \text{Percentage change in LDL-C from baseline to 6 weeks in atorvastatin 40 mg}$$

Azar et al. reported that the between-treatment difference in percentage change in LDL-C at 8 weeks was -10% in favor of ezetimibe/atorvastatin 10/40 mg compared to atorvastatin 40 mg (-20% vs -10%; p-value=0.01) (Azar RR 2010). This is the only study that has assessed the efficacy of ezetimibe/atorvastatin 10/40 mg versus atorvastatin 40 mg among very high-risk patients with stable CAD or CAD equivalent (coronary stenosis >50%, previous myocardial infarction, percutaneous coronary intervention, coronary artery bypass graft surgery, diabetes

mellitus, stroke, peripheral vascular disease) who were taking the potency of the background statins ≤ 20 mg/day of atorvastatin prior to the randomization. Although the evaluation time point for the LDL-C lowering effect in Azar et al. study is at 8 weeks, it is noted that a reduction in LDL-C is usually achieved with all statins as well as ezetimibe as early as 2 weeks, with a maximum response occurring by 4 weeks and maintaining thereafter during continued therapy (ACH-Ezetimibe Product Monograph 2019; Shankar PR 2019). Given that, this study sets -10% as the expected difference in percentage change in LDL-C from baseline to 6 weeks between the treatment groups.

The pooled standard deviation of 19.0% was obtained from the p-value of 0.01 and a total of 50 patients per treatment group reported in the study of Azar et al.; The t-value that corresponds with a p-value of 0.01 and $50 + 50 - 2 = 98$ degrees of freedom is $t=2.627$, considering that the degrees of freedom are given $N_1 + N_2 - 2$, where N_1 and N_2 are the number of study patients per each treatment group. As the t-value is the ratio of the difference in means to the standard error of the difference in means, the standard error is therefore obtained by dividing 10 (treatment difference in percentage change in LDL-C) by 2.627, which gives 3.8066. In turn, the standard deviation obtained from standard error is 19% ($3.8066 / \text{SQRT}(1/50 + 1/50)$).

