Based on this, the number of patients in each treatment group calculated by the formula below is about 57 under the assumption of two-sided significance level $\alpha = 0.05$, power $1-\beta = 0.80$ with a randomization ratio $\lambda = 1$. Considering the dropout rate of 10%, 63 patients for each group and thus, a total of 126 patients will be randomized in this study.

$$n = \frac{(\gamma + 1)(Z_\alpha + Z_\beta)^2 \sigma^2}{\gamma(\mu_t - \mu_c)^2} = \frac{(1 + 1)(1.96 + 0.842)^2(19)^2}{(-10)^2} = 56.69$$

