Repeated style; see Table 26.

Document: Document path and title

Template No.: CCI [REDACTED]

Reference: CCI [REDACTED]

Effective Date: 15Oct2021

Table 100. Proportion of patients achieving LDL-C goal of <55 mg/dL at Week 6 and 12 (with Statin Administration History in FAS)

Repeated style; see Table 20.

Table 101. Proportion of patients achieving LDL-C goal of <55 mg/dL at Week 6 and 12 (with Statin Administration History in PPS)

Repeated style; see Table 20.

Table 102. Proportion of patients achieving LDL-C goal of <70 mg/dL at Week 6 and 12 (with Statin Administration History in FAS)

Repeated style; see Table 20.

Table 103. Proportion of patients achieving LDL-C goal of <70 mg/dL at Week 6 and 12 (with Statin Administration History in PPS)

Repeated style; see Table 20.

Table 104. Percentage Change in LDL-C from Baseline to Week 6 and 12 (without Statin Administration History in FAS)

Repeated style; see Table 26.

Table 105. Percentage Change in LDL-C from Baseline to Week 6 and 12 (without Statin Administration History in PPS)

Repeated style; see Table 26.

Table 106. Percentage Change in HDL-C from Baseline to Week 6 and 12 (without Statin Administration History in FAS)

Repeated style; see Table 26.

Table 107. Percentage Change in HDL-C from Baseline to Week 6 and 12 (without Statin Administration History in PPS)

Repeated style; see Table 26.

Table 108. Percentage Change in non-HDL-C from Baseline to Week 6 and 12 (without Statin Administration History in FAS)

Repeated style; see Table 26.

Document: Document path and title

Template No.: CCI

Reference: CCI

Effective Date: 15Oct2021

Table 109. Percentage Change in non-HDL-C from Baseline to Week 6 and 12 (without Statin Administration History in PPS)

Repeated style; see Table 26.

Table 110. Percentage Change in Triglycerides from Baseline to Week 6 and 12 (without Statin Administration History in FAS)

Repeated style; see Table 30.

Table 111. Percentage Change in Triglycerides from Baseline to Week 6 and 12 (without Statin Administration History in PPS)

Repeated style; see Table 26.

Table 112. Percentage Change in Total Cholesterol from Baseline to Week 6 and 12 (without Statin Administration History in FAS)

Repeated style; see Table 26.

Table 113. Percentage Change in Total Cholesterol from Baseline to Week 6 and 12 (without Statin Administration History in PPS)

Repeated style; see Table 26.

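### SAP 8.3 codes patients on a statin for under 4 weeks and patients on no statin as one 'No' level: no bias, but avoidable residual variance and mislabelled subgroup tables

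*SAP*

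**What the plan says.** SAP 8.3 defines the statin-history factor from one eCRF item with three answers: on a statin for 4 weeks or more, on one for less, and not on one. The last two are merged: "No if 'Is the patient under statin treatment?' is 'Yes, but for less than 4 weeks from today' or 'No". The two-level factor enters the primary ANCOVA (SAP 15.1.2) and the ANCOVAs for the secondary endpoints (15.2.3), and it defines a subgroup (8.5).

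The merging follows the protocol. Inclusion criterion 3(b) and stratum (b) in Protocol 6.3.1 put statin-naïve patients together with those lacking a stable regimen for at least 4 weeks. Stratum (b) is held below 40% of each group.

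The Table 10 shell shows the merged level as "No (<4 weeks or naïve", with separate rows beneath for its two parts. Tables 104 to 117 do not keep the split. Table 104, for example, is titled "Percentage Change in LDL-C from Baseline to Week 6 and 12 (without Statin Administration History in FAS".

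The lipid baseline is the Visit 1 value (SAP 7.2), and neither document describes a washout. On timing, Protocol 9.5 says that LDL-C reduction with statins and ezetimibe is usually achieved "as early as 2 weeks, with a maximum response occurring by 4 weeks".

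**The concern.** Percentage change from baseline means different things in the two kinds of patient. A drug-free patient's change contains the whole effect of starting atorvastatin. A patient already 2 to 4 weeks into a statin shows mainly the further step from that statin to study drug. Baseline LDL-C separates the two poorly, because a given value can be untreated in one patient and treated in another.

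Two things are at stake. The difference between the two kinds goes into the residual variance of the primary model and widens its interval. And the tables that a reader would consult for early combination in untreated patients include some patients who were taking a statin, under a title that says otherwise.

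**Working it through.** **1. The plan's own figure.** Protocol 9.5 plans on a 10-point difference ("this study sets -10% as the expected difference in percentage change in LDL-C from baseline to 6 weeks between the treatment groups") and an SD of 19 ("the standard deviation obtained from standard error is 19"%).
- SD: t for p = 0.01 on 98 df is 2.627; 10/2.627 = 3.807; 3.807/√(2/50) = 19.03.
- Size: n = 2 × (1.96 + 0.842)² × 19²/10² = 56.69, so 57 per arm, with 80.2% power. 56.69/0.9 = 62.99, so 63 randomised.

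The figure reproduces. The SD comes from patients "who were taking the potency of the background statins ≤ 20 mg/day of atorvastatin prior to the randomization". As described, that study had no drug-free patients, so its SD contains no spread between the two kinds.

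**2. How far apart the two kinds are.** Assumed values, not in the documents: a statin at full effect leaves 60% of untreated LDL-C, atorvastatin 40 mg leaves 53%, and ezetimibe multiplies by 0.82. If b is the fraction of untreated LDL-C present at baseline, the expected change is 100 × (0.53/b − 1) on Ato and 100 × (0.53 × 0.82/b − 1) on Eze/Ato.

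| Statin effect already present | b | Ato | Eze/Ato | Gap to drug-free (Ato; Eze/Ato) |
|---|---|---|---|---|
| None (drug-free) | 1.00 | −47.0 | −56.5 | – |
| Half | 0.80 | −33.8 | −45.7 | 13.3; 10.9 |
| Three quarters | 0.70 | −24.3 | −37.9 | 22.7; 18.6 |
| Full | 0.60 | −11.7 | −27.6 | 35.3; 29.0 |

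The −11.7 is close to the −10% on atorvastatin 40 mg in the study cited in Protocol 9.5. The treatment difference also varies: 56.5 − 47.0 = 9.5 points in drug-free patients against 27.6 − 11.7 = 15.9 at full effect. A pooled subgroup estimate therefore depends on the mix.

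**3. Variance added if baseline LDL-C explains none of the gap.** Added variance = f × q(1 − q) × D². Here f is the share of patients in 'No' (0.40, the cap), q is the share of those already on a statin, and D is the gap. Dividing by 19² = 361 gives the increase:

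| D | q = 0.10 | q = 0.25 | q = 0.50 | SD and power at 57 per arm, q = 0.50 |
|---|---|---|---|---|
| 10 | 1.0% | 2.1% | 2.8% | 19.3; 79.2% |
| 20 | 4.0% | 8.3% | 11.1% | 20.0; 76.0% |
| 30 | 9.0% | 18.7% | 24.9% | 21.2; 71.0% |
| 40 | 16.0% | 33.2% | 44.3% | 22.8; 64.8% |

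At q = 0 or q = 1 the increase is zero.

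**4. With baseline LDL-C in the model.** Two simulations compared the planned factor with a three-level one.
- Fixed gap (57 per arm, SD 19 within each kind, q = 0.50, baselines 50 mg/dL apart, 1,500 runs). At D = 30 the residual SD was 20.72 with two levels and 18.94 with three: (20.72/18.94)² = 1.20, with power about 70% against 79%. At D = 20 it was 19.81 against 19.00: a ratio of 1.09, with power about 74% against 78%.
- Proportional response (the step 2 multipliers, 40% in 'No'). The variance of the treatment difference was larger with two levels by a factor of 1.07 to 1.17 if every short-term user has a fully treated baseline, 1.03 to 1.05 with three quarters of the effect present, and 1.00 to 1.02 with half. A second set of runs at full effect reached 1.18. A third, with 90% or 95% of 'No' patients drug-free, gave 1.08 and 1.05.

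In the proportional-response runs where it was recorded, the mean treatment estimate was the same under both models.

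**5. The labels.** Under SAP 8.3 a patient who reports statin use for less than 4 weeks is coded 'No', and so falls in Tables 104 to 117, whose titles say there is no statin history. One such patient makes the titles wrong, whatever the mix.

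**The case against.** The pooling is the protocol's, not a slip in the SAP. It mirrors criterion 3(b) and stratum (b), and Protocol 9.3.1 and 9.3.2 name statin history as the covariate. Adjusting for the stratification factor is standard. Allocation is 1:1 within the pooled stratum, so a reader who infers bias or an inflated type I error would be wrong.

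The larger variance figures need unfavourable conditions. The under-4-weeks level includes patients in their first 13 days, and Visit 1 results may be up to 2 weeks older than the screening visit, so some baselines may predate the statin. The 40% is a cap, not an expectation. A separate under-4-weeks level would itself mix treated and untreated baselines, and the 'No' answer shows only that the patient is not on a statin now, not that the patient is naïve.

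A reader might also infer that the trial is underpowered. The documents do not settle that. One set of proportional-response runs gave pooled-model standard errors of 2.93 to 3.06, below the 19 × √(2/63) = 3.39 implied by the plan; at 3.06, power for 10 points is about 90%. Those runs had less scatter than planned, though: with the kinds separated, 2.70 to 2.89 divided by √(2/63) is an SD of about 15 to 16. If 19 is the SD within each kind, step 3 applies.

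Nor is it right that the pooled subgroup describes no clinical group: it is eligibility group (b). Its definition is stated in SAP 8.3, Table 10 splits it, the subgroup analyses are exploratory (15.3), and SAP 8.2 limits inferential conclusions to the primary endpoint.

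Most of this stands. It does not show that the model should ignore a prognostic baseline level already recorded, and an open definition in 8.3 does not correct the titles of Tables 104 to 117.

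**Conclusion.** The point holds as one of efficiency and labelling, not of validity. Under the assumed proportional response, with the 'No' level at its 40% cap, the pooled factor makes the variance of the treatment difference about 0% to 17% larger than the split would. The upper end needs fully treated baselines in all short-term users and a real mix of the two kinds; with half the effect present the loss is 2% or less. The 17% is not a ceiling: the fixed 30-point gap with an even mix gave 20%. The mix and the gap are unknown, so the actual size cannot be fixed from the documents. The mislabelling of Tables 104 to 117 depends on none of these assumptions beyond at least one short-term user being enrolled.

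**What to change.** - In SAP 8.3, 15.1.2 and 15.2.3, keep the randomisation stratum in the ANCOVA and add the recorded split of the 'No' level (on a statin under 4 weeks versus not on a statin) as a term nested within it. The split should not replace the stratum. At minimum, prespecify this as a sensitivity ANCOVA. That form is preferable if results by arm have already been seen, since the trial is open-label.
- In Tables 104 to 117, show the under-4-weeks and not-on-statin results separately, and retitle the pooled tables as statin under 4 weeks or none.
- State how the stratum maps to the eCRF item. Stratum (b) turns on an unchanged regimen and the item on duration, so a long-term user with a recent dose change could be (b) at randomisation and 'Yes' in the model.

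The cost is SAP wording, extra table rows and one degree of freedom. No new data are needed. The under-4-weeks cell may be too small for more than descriptive results.
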